Systematic reviews examining the effect of digital sepsis alerts have found low diagnostic accuracy and modest improvement in sepsis related outcomes.¹⁵⁻¹⁶ Most existing evidence comes from small, ICU based studies in hospitals in the United States (US). There has been no large-scale study investigating the effects of digital alerts on patient outcomes, particularly in the UK healthcare system.

Using routine clinical datasets, the mechanisms and mediators of effectiveness and consequences of digital alerting in outcomes for patients with sepsis will be assessed. A framework comprised of a series of methods guided by clinical effectiveness research principles will be used to achieve this.

This project specifically focuses on digital alerts used to identify clinical deterioration due to sepsis or serious infectious disease. We will describe these as 'digital alerts' whether they are specific to sepsis or more general EWS.

Previous qualitative research with healthcare professionals has highlighted problems in identification and management of sepsis including limits in professionals' capacity to identify sepsis, difficulties in handover of patients and errors in communication.¹⁷⁻²¹ These studies highlight both the requirement for healthcare professionals to feel confident in their assessment of patients and for clinical and organisations structures to work efficiently to provide optimal patient care. Previous qualitative research with patients has reported on patients' decisions to seek help with symptoms, experiences of hospitalisation and how patients have managed life after surviving sepsis.²²⁻²⁴ Additional studies with caregivers have described the burden on those caring for sepsis survivors and their role in advocating for their loved ones.^{24,25} Another study has looked at the words patients and call handlers use to describe symptoms of sepsis when patients seek help.²⁶ These topics can help to inform how patients and clinicians could use and potentially benefit from the use of digital alerts in hospitals.

The quantitative study will treat the introduction of alerts as a natural experiment and use appropriate methods to analyse routinely collected data to make causal inference.

The qualitative study will include three methods of data collection; observation of healthcare professionals working in hospitals, one-on-one interviews with healthcare professionals and focus groups with patients/carers.

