For the primary analysis we will identify patient hospital encounters where the alert was active and visible to clinicians and use EHRs to identify a cohort of patients who have the same clinical characteristics as the alerting patients, based on routinely recorded vital signs or alerting software. These will act as a control group. Statistical analysis plans will be dependent on the implementation approach in individual Trusts. In line with the approaches recommended in the MRC guidance, methods to be included are those where the factors which determine the exposure can be measured: matching; regression adjustment; and propensity score approaches. We will also utilise methods which are best suited for adjusting for pre-implementation trends including interrupted time series. All analyses will be adjusted for clustering of patients within wards or Trust sites.

Secondary analysis

We will use a controlled multilevel interrupted time series regression to examine trends in mortality for patients with codes defined as 'suspicion of sepsis' and a more robust definition of sepsis. utilise this method to examine unintended consequences identified above.

Sensitivity analysis

We will consider mortality following an A&E attendance for stroke and/or trauma as an unrelated outcome in a sensitivity analysis. Although these patients may trigger an alert, we would not expect their treatment to be different after the introduction of the alert as they are likely to be identified rapidly on arrival. This will enable an assessment of the specificity of effect. This will be included in primary and secondary analysis. These conditions will be included as controls in controlled interrupted time series.

Study Sequence and Duration

Data extraction will commence in March 2022 and be completed by May 2022. Analysis will be completed by December 2022.

7.3 WorkStream 3 – To explore the views and experiences of healthcare professionals and patients/carers on the use of digital sepsis alert systems in hospitals.

Methodology

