19. APPENDIX

Comparison of different alerting algorithms across five NHS hospital Trusts: Descriptive analysis of patient characteristics and frequency of process and clinical outcomes

A mainly descriptive project, with some modelling and statistical analysis, comparing groups of patients. Main cohort: patients (18+) who alerted and patients who were discharged with a SoS code (ICD-10). Time period: introduction of EHRs to March 2021.

General data description: patient information, admission & discharge information, antibiotic prescribing, microbiology tests ordered and results, ICU admission, alert details (including location of alert) Introduction

1. Background/rationale

National guidelines for screening for sepsis have been implemented in NHS Trusts. As hospitals in England introduce electronic health records, different screening algorithms have been adopted (summarised in Table 1).

		NEWS	Red Flag	SJSA	Combination*	
Trust Question re infection as part of EHR alert		UCLH	CW & RB	ICHT	OUHT	
		Yes	Yes	No	Yes	
Lungs	Respiratory rate	Yes	Yes	Yes	Yes	
	O ₂	Yes	Yes	No	Yes	
CV	Heart Rate	Yes – low & high	Yes – high only	Yes – high only	Yes – low & high	
	Blood Pressure	Yes – low & high (SBP)	Yes – low only (SBP)	Yes – low only (SBP)	Yes – low & high (SBP)	
Temperature		Yes – low & high	Amber alert – low	Yes – low & high	Yes	
Level of cor	nsciousness	Yes (VPU)	Yes (VPU)	No	Yes (VPU)	
Fluid balan	ce	No	Yes	No	No	
Lactate		No	Yes	No	Yes	
Bilirubin		No	No	Yes	No	
Creatinine		No	No	Yes	Yes	
White blood cell count		No	No	Yes	Yes	
AKI		No	No	No	Yes	

Table 1 Alert algorithms in different Trusts included in the study.

*OUHT use red flag sepsis and NEWS2

In this study we will compare the characteristics of patients who alert, the frequency of alerts across time (staff shifts, weeks and months) and patient outcomes. In addition, we will describe the completion of process measures associated with treatment of patients with sepsis. Process measures we have included are: blood cultures, lactate measure and IV-antibiotics. It is important to note that not all patients who alert will actually have clinically defined sepsis. Therefore, not all process measures will have been completed, particularly IV antibiotics. We will capture this variation in cohort and process measures across NHS Trusts.

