Although we would expect digital sepsis alerts to have the main impact on patients with sepsis, and this is the stated aim of many commercial sepsis alerts, administrative data may not be sufficient to identify patients with sepsis, particularly as national guidance on sepsis coding changed in 2014, effectively increasing the number of patients with an official diagnosis of sepsis.[5] In addition, efficient clinical response to digital sepsis alerts may result in a decrease in disease progression to sepsis. We have therefore decided to focus on outcomes of patients with an ICD-10 Suspicion of Sepsis code.[6] We will use interrupted time series with a control to determine the impact of the introduction of alerts on patient outcomes and process measures. Interrupted time series is an important methodology which allows

before and after comparisons whilst taking trends prior to the intervention into account and is considered a robust methodology for analysing natural experiments. However, confounding due to other 'interventions' occurring at the same time as the intervention of interest can confound interpretation. A control is an appropriate method to take this type of confounding into account.[7]

For the control we have selected patients with an ICD-10 code included in the category gastrointestinal bleeding. This is a suitable control as we would not expect these patients to trigger a sepsis alert and outcomes should not be impacted by patients being identified as having sepsis. The ICD-10 codes included in this indicator are shown in Table 1.

Objective - Quantify the impact of a digital alert on the key patient outcomes and process outcomes

Primary outcome: in-hospital mortality within 30 days

Secondary outcome: length of stay

ICU admission

2.Methods

2.1Study design

Setting - Describe the setting, locations, and relevant dates, including periods of recruitment, exposure, follow-up, and data collection

This is a time series analysis across five NHS Trusts in England and one NHS Trust in Wales. The period of study is 1st April 2010 to 31st March 2021.

2.2 Participants - the eligibility criteria, and the sources and methods of selection of participants All adult (18+) inpatients admitted as emergency patients between 01/04/10 and 31/03/2 are initially eligible for inclusion in the study.

Intervention group: patients with a discharge diagnosis including one of the SoS sepsis codes at any place in the diagnosis.

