Control group: patients with a discharge diagnosis which is use by the NHS to identify patients with a 'Fall' code.

2.3 Variables - Clearly define all outcomes, exposures, predictors, potential confounders, and effect modifiers. Give diagnostic criteria, if applicable

Primary outcome: in-hospital mortality within 30 days of admission **Secondary**:

- In-hospital mortality within 7 days of admission
- Length of stay
- ICU admission

Intervention: Introduction of digital alerts or changes in screening programmes

Potential confounders:

- Age
- Sex
- · Comorbidities which increase the risk of poor patient outcomes
- Ethnicity
- Season

Sub-group analysis

Age-groups

Patients who are immune-compromised

2.4 Data sources/ measurement - For each variable of interest, give sources of data and details of methods of assessment (measurement).

Data are routinely collected data to comply with NHS requirements for Secondary Users Service. Data is quality checked by individual Trust before it is submitted to the NHS, and is compiled into Hospital Episode Statistics which have been widely used for research in the UK.

As part of the NIHR-Health Informatics Collaborative data managers at each trust shared data through a secure data platform. All data was quality checked and processed by the data warehouse team at ICHT.

Bias - Describe any efforts to address potential sources of bias

We are using a control intervention group to address the main source of bias – that is that for four of the six Trusts alerts were introduced at the same time as digital alerts.

Study size

Six NHS Trusts were recruited to take part in the study. The number of patients included in the study is determined by the number of patients who were discharged with an SoS ICD-10 code. The power to detect differences will be determined post-hoc.

Quantitative variables - Explain how quantitative variables were handled in the analyses. If applicable, describe which groupings were chosen and why

Ethnicity – ethnicity coding is based on recorded ethnicity using NHS ethnicity codes. Due to small groups of some ethnic groups we will combine into standard combinations for statistical comparisons. Full details of ethnic groups are included in the supplementary materials.

Age – We broke age into 10-year age groups. For statistical comparisons we combined smaller groups. Full details are included in the supplementary materials.

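### The impact study assumes its control patients would not trigger the alert; the protocol does not support this, so the controlled time series may be contaminated to an unknown degree

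*Protocol*

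**What the plan says.** The Appendix study on the impact of alerts (Protocol, Appendix, 1.1 Background/rationale) uses an interrupted time series with a control condition. It names the condition as follows: "For the control we have selected patients with an ICD-10 code included in the category gastrointestinal bleeding". It defends the choice on two grounds. The first is "This is a suitable control as we would not expect these patients to trigger a sepsis alert". The second is that "outcomes should not be impacted by patients being identified as having sepsis".

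Other places bear on these grounds:

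- Section 7.2, Sensitivity analysis, uses stroke and/or trauma as controls in the controlled time series and argues differently: "Although these patients may trigger an alert, we would not expect their treatment to be different after the introduction of the alert".
- Table 1 of the Appendix descriptive study lists the inputs to each algorithm, including a row headed "Question re infection as part of EHR alert". The entry is Yes for UCLH, for CW & RB and for OUHT, and No for ICHT.
- The descriptive study's statistical methods (association between alerting and coding) refer to one Trust whose alert is not specific to sepsis.
- Section 5 defines the intervention broadly: "We will describe these as 'digital alerts' whether they are specific to sepsis or more general EWS".
- The impact study's participants section names a different control: "Control group: patients with a discharge diagnosis which is use by the NHS to identify patients with a 'Fall' code".

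**The concern.** A control series in this design should feel the co-interventions, here mainly the arrival of electronic health records, but not the alert itself. The first ground for the control says that these patients stay outside the alert's reach. If they do not, and if alerting changes what happens to them, the change in the control series contains part of the alert's own effect, and comparing the two series takes that part out of the estimate.

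The control is the study's stated remedy for its main source of bias, and the primary outcome, 30-day in-hospital mortality, is modelled against it separately by Trust. Contamination could also vary with how specific each algorithm is to infection. That would affect the comparison of alerts under objective 4.1.

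**Working it through.** **Step 1. Is the no-trigger premise supported?** Table 1 of the descriptive study, read across its four algorithm columns:

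| Input | NEWS (UCLH) | Red Flag (CW & RB) | SJSA (ICHT) | Combination (OUHT) |
|---|---|---|---|---|
| High heart rate | Yes | Yes | Yes | Yes |
| Low systolic pressure | Yes | Yes | Yes | Yes |
| Lactate | No | Yes | No | Yes |
| Infection question | Yes | Yes | No | Yes |

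The two inputs common to all four are not specific to infection. That acute bleeding can disturb them is a clinical inference, not something the protocol states. The descriptive study also says that some patients who alert do not have sepsis. Nothing in the protocol gives an alert rate for bleeding, falls, stroke or trauma patients. The premise is therefore unsupported, and section 7.2 does not rely on it for its own controls.

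**Step 2. Is the second ground secure?** Alerting alone does no harm to the comparison; control outcomes must also change. Both the Appendix and section 7.2 say this is not expected. However, the unintended-consequences part of section 7.2 plans to monitor intravenous antibiotics in patients discharged with neither an SoS code nor another infection code, so treatment change outside the SoS group is regarded as possible. Section 7.2 also gives prevention of deterioration in general as the main purpose of early warning systems. The Appendix wording covers only patients identified as having sepsis, not those flagged by a general deterioration score.

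**Step 3. How large could the bias be?** The protocol gives no figure to reproduce. Inputs for an illustration:

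- Risk ratio in SoS patients: 0.77, from the 23% lower risk of 30-day death reported for ICHT (Appendix, 1.1). That estimate came from a different design.
- c, the share of control-group risk exposed to alerting: not in the documents; assumed 0 to 50%.
- x, the alert's effect in exposed controls relative to SoS patients: not in the documents; assumed 0, 0.5 or 1.

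Formulas: RR_control = 1 − c·x·0.23; estimated RR = 0.77 / RR_control; share of log effect lost = 1 − ln(estimated RR) / ln(0.77).

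| x | c | RR_control | Estimated RR | Log effect lost |
|---|---|---|---|---|
| 0 | any | 1.000 | 0.770 | 0% |
| 0.5 | 10% | 0.9885 | 0.779 | 4.4% |
| 0.5 | 20% | 0.977 | 0.788 | 8.9% |
| 1 | 10% | 0.977 | 0.788 | 8.9% |
| 1 | 20% | 0.954 | 0.807 | 18.0% |
| 1 | 50% | 0.885 | 0.870 | 46.7% |

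The sign depends on x. If alerts harmed controls, for example with RR_control = 1 + 0.10 × 0.23 = 1.023, the estimate would be 0.77 / 1.023 = 0.753, further from no effect.

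**Step 4. Does the control alert rate alone bound the loss?** No. Suppose only half of SoS risk is exposed, with RR 0.77 in those exposed. The SoS ratio is then 1 − 0.5 × 0.23 = 0.885. With 10% of control risk exposed and equal benefit, the estimate is 0.885 / 0.977 = 0.906, and 19.0% of the log effect is lost, more than the 10% exposure. The control rate has to be read against the SoS rate, and even then the loss depends on x.

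**The case against.** The best defence is that the rationale has two legs. If control outcomes are unaffected, alerting in controls costs nothing, and the documents twice say that no effect is expected. Section 7.2 gives a reason for stroke and trauma: such patients are likely to be recognised quickly on arrival. This stands, and it is why the bias is a possibility and not a result.

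A reader might infer that Table 1 and section 7.2 show the control patients alerting, and that the design therefore removes part of the effect it seeks. The documents do not support that. Table 1 lists inputs, not who alerts, and three of its four columns include an infection question that may limit alerting in controls. Section 7.2 speaks of stroke and trauma, not bleeding or falls. The inference from bleeding to abnormal vital signs also has no bearing if falls is the control.

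It is also fair that ICHT, the only column without an infection question, is the English Trust where alert and records system did not arrive together, so it least needs a control for that confounder. The concern is not confined to ICHT, though. It also applies to the Trust with no sepsis-specific alert.

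Finally, section 7.2 lists controlled time series under secondary analysis. The Appendix nevertheless uses it for the primary outcome, so the point is not peripheral.

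**Conclusion.** The concern holds as a limit on what the controlled estimate can support. The protocol's claim that control patients would not trigger an alert is not backed by its own material, and its fallback, that outcomes are unaffected, is an assumption that its list of unintended consequences leaves open. It does not follow that the estimate is biased, by how much, or in which direction. Attenuation requires alerts to help control patients; harm would push the estimate the other way; no outcome effect means no bias.

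Under the assumptions of RR 0.77, equal benefit and 10% to 20% of control risk exposed, about 9% to 18% of the log effect is lost. Those exposure shares are assumed. They are not estimates for these Trusts.

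**What to change.** 1. First reconcile which control condition applies: the Appendix names both gastrointestinal bleeding and falls, and section 7.2 names stroke and/or trauma.
2. Delete the no-trigger claim and rest the rationale on control outcomes not being affected by the alert, stated as an assumption.
3. Exclude admissions carrying an SoS code from the control series. SoS codes count in any diagnostic position and no rule covers patients with both codes, so one admission could fall in both series.
4. For each Trust with a digital alert, report the alert rate after go-live in control patients beside that in SoS patients, using the alert indicator in section 8 (WS2). The impact study's data description lists no alert flag, so linkage may be needed. The paper-based Welsh Trust falls outside this table.
5. Where the control rate is not small relative to the SoS rate, and in the Trust without a sepsis-specific alert, report the uncontrolled series beside the controlled one and say that the controlled estimate may be contaminated. Define what counts as small before outcomes are modelled.

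The control should not be chosen by lowest alert rate alone, nor allowed to differ between Trusts for that reason. It must still share the effects of the records system, and differing controls would weaken the comparison across Trusts.

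The cost is one extra table, some linkage work and a second set of estimates.

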The study will collect data on patient outcomes prior to the introduction of the alert for a maximum of five years and up to three years post the duration of the alert. We may have to use shorter time periods for certain Trusts.

Sampling Strategy

We have identified five digitally mature NHS Trusts in England, each operating a digital sepsis alerts. In addition, we are working with a Trust in Wales which is still paper based.

Methods of Data Collection

A detailed data specification and data dictionary will be compiled, with associated SNOMED codes for each observation. All data items are routinely collected and recorded in patient electronic records. All data will be de-identified. We will use the NIHR-HIC data infrastructure to enable data transfer. Please see Section for more details.

Outcomes

The primary outcome will be **all-cause in-hospital mortality within 30 days**. Secondary outcomes (including process measures):

- Transfer to ICU
- Length of stay
- Readmission within 30 days
- Administration of IV antibiotics
- Venous blood tests including lactate and white blood cell count
- Blood cultures ordered

The primary reason for the introduction of EWS systems, including digital alerts, is to prevent avoidable clinical deterioration. Mortality is a key measure of clinical deterioration and the majority of EWS have been validated by assessing their ability to predict mortality. Mortality is recorded in hospital patient records and reported as part of the Secondary Users Service (SUS). It is therefore a reliable and commonly used measure of clinical deterioration. Transfer to ICU is often used as an additional measure of clinical deterioration and is available in EHRs.

Length of stay and readmission within 30 days are important indicators of patient experience and are key targets for hospitals. The aim of early recognition of sepsis is to enable prompt and appropriate treatment. We will therefore assess whether the introduction of digital alerts has impacted on appropriate treatment.

Assessment of unintended consequences

Based on discussion in the Sepsis Big Room clinical teams are concerned about potential increases in unnecessary treatment as an unintended consequence of digital alerting. We will consider four potential measures of unintended consequences:

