2.1 Study design & Setting

This is a cross sectional study across five NHS Trusts in England. The period of study is 1st February 2019 to 31st January 2021, divided into two years starting 01/02/19 and 01/02/20 to consider the impact of Covid-19. The time period was selected based on the latest introduction of electronic health records across the five NHS Trusts and to separately consider patients with Covid-19 affecting the pattern of sepsis alerts.

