
Quantifying the impact of a digital sepsis alert on key patient outcomes and process

measures.

We will use interrupted time series with a control to determine the impact of the introduction of alerts on patient outcomes and process measures

Main cohort: patients (18+) with an SoS ICD-10 code (intervention group) at discharge OR a falls ICD-10 code (control group).

Time period: April 2010 to March 2021

General data description: patient information, admission & discharge information, A&E information and ICU admission if possible

1.Introduction

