Length of stay - length of stay, measured in hours, was determined from the date and time of admission and discharge recorded in the patient record. For this descriptive study we will quantify length of stay for patients who are discharged alive.

Mortality – mortality was based on discharge destination recorded. For the purposes of this study only inhospital mortality was available for all NHS trusts.

Missing data

Patient admissions will not be excluded if patient data is missing, an additional category of missing will be included for age, gender, ethnicity and deprivation. As part of quality checks we will confirm whether there are any patterns in missing data.

Statistical methods

(a) Describe all statistical methods, including those used to control for confounding

Descriptive analysis

We will describe trends in patient mix over time using graphical methods, we will use time series to determine if there were changes in patient mix, including sub-groups of patients, patients with SoS and falls patients.

We will use break point approaches to identify potential key points in time where changes occurred. This will aid in interpretation of results.

Comparative analysis

We will use interrupted time series with a control, adjusted for patient case mix and season. Each Trust will be modelled separately as the introduction of sepsis alerts and electronic health records is different for each Trust. Comparisons will be made between the change in slope and step change in counts.

(b) Describe any methods which will be used to examine subgroups and interactions

Within each model we will separately consider subgroups when we perform our analysis. We will consider a priori interactions.

(c) Explain how missing data will addressed

Missing data will be included as a category on its own for factors such as ethnicity and deprivation. We will inspect data to identify periods of missing data, and consider imputation.

ICD-10 Code	ICD-10 Description
1850	Oesophageal varices with bleeding
K226	Gastro-oesophageal laceration - haemorrhage syndrome K228 Other specified diseases of oesophagus
K250	Gastric ulcer, acute with haemorrhage
K252	Gastric ulcer, acute with both haemorrhage and perforation
K254	Gastric ulcer, chronic or unspecified with haemorrhage K256 Chronic or unspecified Gastric ulcer with both haemorrage and perforation
K260	K260 Duodenal ulcer, acute with haemorrhage
K262	K262 Duodenal ulcer, acute with both haemorrhage and perforation

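### The impact time series runs 14 months past the protocol's own Covid-19 split date with no pandemic handling, so a pandemic change not shared by the control can be read as an alert effect

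*Protocol*

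**What the plan says.** Section 10 of the protocol refers the reader to the Appendix for the detailed statistical plans, so the Appendix is where the model is fixed. Four elements matter.

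- **Impact study, window.** The heading block gives "Time period: April 2010 to March 2021", and the setting paragraph repeats it: "The period of study is 1st April 2010 to 31st March 2021".
- **Impact study, model.** It is an interrupted time series with a control, adjusted for case mix and season. Results are read as a change in slope and a step change. The listed confounders are age, sex, comorbidities, ethnicity and season. On the unit of analysis: "Each Trust will be modelled separately as the introduction of sepsis alerts and electronic health records is different for each Trust". Covid-19 is not mentioned anywhere in this study's plan.
- **Descriptive study.** It has a Covid-19 objective, and its 24 months are "divided into two years starting 01/02/19 and 01/02/20 to consider the impact of Covid-19". On the choice of window it says: "The time period was selected based on the latest introduction of electronic health records across the five NHS Trusts".
- **Section 7.2.** Outcome data are to be collected "prior to the introduction of the alert for a maximum of five years and up to three years post the duration of the alert". The only flexibility is downwards: "We may have to use shorter time periods for certain Trusts".

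**The concern.** The protocol recognises in one study that the pandemic disturbs sepsis alerting, and separates that year. The other study, which carries the causal question and 30-day in-hospital mortality, runs through the same months without separating them.

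A Trust that introduced its alert before February 2020 has all its pandemic months after the interruption. A late disturbance in the SoS series then competes with the alert for the same two coefficients. The control removes only what it shares with the SoS series. The adjustment set contains nothing that distinguishes the pandemic period.

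A second, separate question is which stretch of data each Trust contributes. Section 7.2 sets a limit relative to the alert date, the Appendix gives fixed calendar dates, and the two are not connected. The pre-alert trend to be projected forward depends on which governs.

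**Working it through.** **Windows**

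- Impact study: April 2010 to March 2021 = 11 × 12 = 132 months.
- Section 7.2 limit: (5 + 3) × 12 = 96 months per Trust. The calendar span is 132 − 96 = 36 months longer.
- Months from the 1 February 2020 split to 31 March 2021: 11 + 3 = 14.

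**Share of post-alert months after the split**

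The documents give no alert dates, so these go-live dates are assumptions. February 2019 is the latest one suggested by the descriptive study's choice of window.

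| Assumed go-live | Post-alert months to March 2021 | After the split | Share |
|---|---|---|---|
| April 2014 | 84 | 14 | 17% |
| April 2016 | 60 | 14 | 23% |
| April 2018 | 36 | 14 | 39% |
| February 2019 | 26 | 14 | 54% |

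**Effect on the planned coefficients**

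The model for the SoS series relative to control, in month t with go-live t0, is

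log(ratio) = b0 + b1·t + b2·post + b3·(t − t0)·post.

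The step is exp(b2) and the slope change per month is exp(b3). Input: 132 months without noise, flat background, no alert effect, go-live February 2019, and an SoS-only mortality rise from February 2020. The size of the rise is an assumption, since the documents give none. Poisson fit:

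| Assumed rise | Spurious step | Spurious slope per month | Fitted ratio in last month (step × slope^25) |
|---|---|---|---|
| 10% | 0.984 | 1.0055 | about 1.13 |
| 20% | 0.970 | 1.0104 | about 1.26 |
| 40% | 0.949 | 1.0192 | about 1.53 |

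The two effect measures err in opposite directions: an apparent immediate benefit, then an apparent worsening.

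**Dependence on go-live**

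With a 20% rise, fitted by least squares on the log scale:

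| Assumed go-live | Step | Slope per year |
|---|---|---|
| April 2014 | 0.956 | 1.022 |
| April 2016 | 0.948 | 1.040 |
| April 2018 | 0.946 | 1.091 |
| February 2019 | 0.968 | 1.134 |

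**Does the section 7.2 limit cure it?**

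Thirty-six months after go-live passes 1 February 2020 whenever go-live is later than 1 February 2017. Under the limit, the pandemic months remaining are 0 for April 2014 and April 2016, 2 for April 2017, and all 14 for April 2018 and February 2019.

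**With a pandemic term**

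Adding b4·P(t), with P = 1 from February 2020, returns step and slope to 1.000 for every go-live tried. Ending the series at 31 January 2020 does the same. This exact recovery reflects a noise-free input in which the pandemic acts as a constant shift.

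**The case against.** The strongest case against the point has several parts.

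- **The control.** A controlled series cancels shocks common to both groups, so only differential change biases it. This stands. A reader might infer that pandemic mortality is bound to be read as an alert effect, or that the control cannot absorb it. The documents do not support that. They give no size for the differential change, and the SoS code list is not reproduced, so whether it captures Covid-19 admissions cannot be checked. They also give no reason to expect both groups to be affected alike. The control itself is named as gastrointestinal bleeding in one place and falls in others.
- **Break-point and case-mix checks.** These could flag early 2020. They are listed as descriptive, to help interpretation, and put no term in the model.
- **A simple level shift.** A reader might fit a level change only and report spurious ratios of 1.05, 1.10 and 1.19 for a February 2019 go-live, or see a true 0.77 read as 0.81, 0.85 and 0.92. Those figures do not describe the planned analysis, which compares slope and step. The level-only result even reverses for April 2016, to 0.980, 0.961 and 0.925.
- **The worst case.** The 54% share belongs to one assumed date, taken from electronic record introduction. The Appendix says one Trust's alert was not part of that introduction, and section 7.2 describes the Welsh Trust as still on paper. The point therefore cannot be asserted uniformly for all six.
- **The window.** A reader might infer that every Trust contributes 132 months and that the counterfactual is undefined. The calendar dates may instead be an envelope around Trust-specific windows, because patients are only initially eligible within them. The text does not say so.
- **Status.** Section 7.2 places controlled time series in SoS-coded patients under secondary analysis, although the Appendix gives this study a primary mortality outcome.

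**Conclusion.** The point holds as a risk built into the plan as written. The series includes 14 months beyond the descriptive study's own Covid-19 split, and nothing in the comparative model separates them. Because the Appendix is presented as the detailed plan and fixes window, confounders and model, this is more than detail left for later.

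The size is conditional. With a February 2019 go-live and an SoS-only rise of 10% to 40%, the spurious slope is 1.0055 to 1.0192 per month and the spurious step 0.984 to 0.949. The pandemic share of follow-up falls to 14/60 for an April 2016 go-live and 14/84 for April 2014, and the slope bias shrinks with it. Direction depends on which measure is read, and in a level-only fit also on go-live. A differential fall in mortality would reverse the signs. The figures rest on assumed dates, an assumed constant shift and noise-free data.

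The mismatch between section 7.2 (96 months) and the Appendix (132 months) is a separate matter of reconciliation. Resolving it would not by itself deal with the pandemic for late-adopting Trusts.

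**What to change.** 1. In the impact study's comparative analysis, pre-specify a pandemic-period-by-group term from 1 February 2020, as a level and, where estimable, a slope. Add a sensitivity analysis ending on 31 January 2020. The reverse order, with the truncated series as main analysis and the pandemic term as sensitivity, is equally defensible if chosen in advance.
2. State whether April 2010 to March 2021 is only a calendar envelope for Trust-specific windows of at most 60 months before and 36 after the alert, or whether it replaces the section 7.2 limit. Use the same statement in both places.

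The cost is protocol wording and some precision. In a Trust going live in February 2019, truncation leaves 26 − 14 = 12 post-alert months. The pandemic term keeps all 26, but the alert's slope must then be separated from the pandemic shift with only 12 post-alert months before the split. Intervals will be wider there and little changed in early adopters.
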